The initial part of the study design is to evaluate the effectiveness of the brief early intervention for substance use. Analyses will be based upon measures of substance use and ADHD symptoms, measured at baseline and 6 month assessments. The analytical plan addresses the multiple measurements on the same participant, with a cautious eye toward any concerning missing data issues. We expect drop out to be minimal as has been the case in our decade of experience with treatment studies of ADHD teens. To date, our collective dropout rate is below 5% per year. *Studies conducted in Miami-Dade County with Hispanic adolescents who display behavior problems and emergent substance use report slightly lower retention, with 16-19% attrition (Pantin et al., 2009; Prado et al., 2007). In our studies, data loss has also been relatively low; should there be a missing data issue, we suspect that the last observation carried forward method (LOCF) will be a satisfactory strategy to use. However, we are well aware of other methods and would also use the Mixed-Effects Model Repeated Measures (MMRM) which is more robust to biases and provides better control on type I and II error.*

A careful assessment of data quality will be undertaken as data are being collected and entered, with the usual set of appropriate value, range and logic checks. Data will be collected and handled in a manner that satisfies all local and national requirements for personal privacy, specifically PHI, and data security. Prior to analyzing outcome, comprehensive assessments of data quality, including examination of requirements for the assumptions underlying outcome analyses (i.e., normality, linearity, independence, homogeneity of variance) will be undertaken. Should these assumptions not be met, we will adjust the analytical approach or use transformations as appropriate. We will also apply standard methods for outlier detection (e.g., analysis of leverage statistics, residuals, and df Betas), and use robust statistical significance tests if variance is heterogeneous or re-specify model terms if assumptions of linearity are violated.

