Power Analysis: For Aim 1, previous evaluations of BEI report a large effect of treatment on days of alcohol use (d=2.67; Winters et al., 2007). A sample size of 300 (G*Power 3.1.2 software), with alpha of 0.05 for a two-tailed test, will provide power = 0.96 to detect a small treatment effect size of 0.25 if there are no drop outs. Assuming a maximum dropout rate of 15%, as shown in previous studies with Hispanic adolescents with behavior problems (Pantin et al., 2009; Prado et al., 2007), the power drops slightly to 0.90. We also plan to measure the impact of concurrent medication use on treatment effect. For this analysis there are now two groups of participants, those currently using stimulant medication and those not using stimulant medication. The sample size of 300 with a maximum drop-out rate of 15% will provide .90 power to detect an interaction effect of medication, assuming a small pre-test to post-test correlation among measures (r = .25). For Aim 3, a sample size of 150 with a maximum drop-out rate of 15% will provide .90 power for a treatment effect size of .40, which is adequate considering that most ES for similar treatments range between .40 and .80 (Waldron & Turner, 2008). Thus, the sample should be sufficient to detect significant effects of treatment as well possible prediction models.

c. Potential Risks

Risk: Participants may experience mild and transitory psychological discomfort from completing research measures that deal with emotionally laden material, including reporting on illicit drug use and other antisocial or illegal behaviors, which may be uncomfortable for some participants. **Procedure:** We will inform participants of the NIH Confidentiality Certificate prior to collecting any data for the study, which will shield the research data from a subpoena or court order. In addition, participants and their parents will be advised to ask questions of study personnel if confidentiality is of a concern, and to refrain from answering questions that cause them personal distress.

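### The 15% maximum dropout in the power analysis lies below the 16-19% that the plan reports for the same two studies, and the two Aim 1 powers (.96 and .90) do not match each other at printed precision

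*Combined protocol and SAP*

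**What the plan says.** The Power Analysis paragraph, under Hypotheses and Data Analysis, gives the Aim 1 inputs as "A sample size of 300 (G*Power 3.1.2 software), with alpha of 0.05 for a two-tailed test", which "will provide power = 0.96 to detect a small treatment effect size of 0.25 if there are no drop outs". It then allows for loss: "Assuming a maximum dropout rate of 15%, as shown in previous studies with Hispanic adolescents with behavior problems", with two studies cited, and concludes that "the power drops slightly to 0.90".

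The same 15% is applied to two further claims in that paragraph: .90 power for the medication interaction (N=300, with a pre-post correlation of .25), and .90 power for Aim 3 (N=150, effect size .40).

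The opening paragraph of the Analyses section cites the same two studies for a different figure: "Studies conducted in Miami-Dade County with Hispanic adolescents who display behavior problems and emergent substance use report slightly lower retention, with 16-19% attrition". That paragraph also puts the centre's own dropout below 5% per year, and the Potential Risks section repeats a rate under 5%.

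Two inputs are not given for the Aim 1 main effect. The paragraph does not say whether .25 is a standardised mean difference (d), a standardised mean change (dz) or Cohen's f. The correlation of .25 is stated only for the interaction. The Aim 1 paragraph describes a one-group comparison of baseline with 6 months by repeated-measures GLM with covariates.

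**The concern.** A maximum attributed to two studies cannot be lower than every value reported for them. One of the two statements is wrong as written, and the lower figure is the one behind all three dropout-adjusted powers.

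The step from .96 to .90 also looks too large for a 15% loss. If it is, at least one printed power was obtained on a different basis from the other, and a reader cannot tell which because the effect-size type and the correlation are missing. At stake is whether the planning figures can be traced and checked, and whether the loss allowance is as cautious as it is presented to be.

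**Working it through.** **Inputs.** From the Power Analysis: N=300, two-sided alpha .05, effect size .25, power .96 without loss, 15% loss, power .90 with loss. From the Analyses section: 16-19% attrition. Assumption: r=.25 is carried over to the main effect from the interaction statement.

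**Step 1. Sample sizes after loss.**
- 15%: 300 × .85 = 255
- 16%: 300 × .84 = 252
- 19%: 300 × .81 = 243
- Aim 3 at 15%: 150 × .85 = 127.5, about 128
- Aim 3 at 19%: 150 × .81 = 121.5, about 122

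**Step 2. Try to reproduce the plan's figures.** For a one-group pre-post comparison, use the paired t test with dz = d/√(2(1−r)), noncentrality dz√n and n−1 degrees of freedom. With d=.25 and r=.25, dz = .25/√1.5 = .204. Results for d=.25 under several correlations:

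| r | N=300 | N=255 (15%) | N=252 (16%) | N=243 (19%) |
|---|---|---|---|---|
| 0 | .863 | .803 | .798 | .784 |
| .10 | .896 | .842 | .838 | .825 |
| .25 | .941 | .901 | .898 | .887 |
| .30 | .954 | .919 | .916 | .907 |
| .50 (so dz=.25) | .991 | .978 | .977 | .973 |

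The r=.25 row gives the stated .90 but falls 1.9 points short of .96. The r=.30 row is within 2 points of both stated values but rounds to neither.

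**Step 3. Test the pair without choosing d or r.** Solve for the dz that gives one stated power, then read off the other.
- .96 at N=300 needs dz=.215. Power at N=255 is then .928. Allowing for rounding (.955 to .965), it is .920 to .935, which never rounds to .90.
- .90 at N=255 needs dz=.204. Power at N=300 is then .940. Allowing for rounding (.895 to .905), it is .937 to .944, which never rounds to .96.
- With dz=.215, power falls to .90 only at about N=230, a loss of (300−230)/300 = 23%.

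The mismatch is .928 against .90 at N=255 and .940 against .96 at N=300. With rounding of the printed values, that is roughly 2 to 4 points.

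**Step 4. Cost of the dropout correction for Aim 1.** From 15% to 19% loss, with d=.25 and r=.25: .901 − .887 = 1.4 points. With .96 at N=300 taken as exact: .928 − .916 = 1.2 points. Working from unrounded powers and allowing for rounding of the stated values, the cost is about 1.2 to 1.5 points.

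**Step 5. Indication for Aim 3.** A three-arm F test at alpha .05 gives .985 at 128 and .981 at 122 if the effect is f=.40, and .50 and .48 if it is f=.20. The dropout change moves power by about 0.4 to 2 points in either case. The interaction power was not recomputed, because its effect size and group split are not stated.

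**The case against.** The strongest reply has four parts.

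First, the power pair may be loose reporting and not an error. With d=.25 and the plan's own r=.25, a standard calculation gives .941 and .901. An omnibus F test with f=.25 and four numerator degrees of freedom gives .949 and .905. This stands in part. A reader might infer that no method at all could yield both figures, and the documents do not support that, because they name neither the effect-size type nor the exact test used. For the two-time-point comparison described under Aim 1, however, Step 3 shows that the pair does not cohere whatever the effect size or correlation. The four-degree-of-freedom test does not match that comparison, and it also misses .96.

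Second, 15% is already generous beside the centre's own rate below 5% per year, given a 6-month endpoint. The follow-up length behind the 16-19% is not in the documents, so 19% may be too severe. This stands as a possible reason to choose 15%. It does not rescue the text, which rests the 15% on the two external studies and not on the centre's history.

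Third, the correction hardly changes anything. This stands for Aim 1.

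Fourth, reuse of the 15% does not show that the other powers fail. This also stands. A reader might infer that the interaction and Aim 3 conclusions fall with it, but for Aim 3 the indicative change is at most about 2 points, and for the interaction nothing has been shown. The meaning of the .40 matters far more to Aim 3 than 15% against 19%.

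**Conclusion.** The attribution is wrong as written: 15% is called a maximum on the strength of two studies that the same plan reports at 16-19%. The two Aim 1 powers differ from a mutually consistent pair by about 2 to 4 points, assuming a two-sided paired comparison of baseline with 6 months.

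Neither point makes Aim 1 underpowered under readings close to the stated figures. At 19% loss, power is .887 with d=.25 and r=.25, .916 if .96 is taken as exact, and .973 if .25 is dz, in which case the printed figures are conservative. Power near .78 at 19% loss arises only if d=.25 is combined with r=0. That reading gives .863 at N=300 and so does not fit the plan's own .96. This spread is wider than the effect of the dropout correction, so the unstated effect-size type and correlation are the larger gap in the power statement.

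This is a correction to the documentation of planning figures. It gives no reason to change the sample size or the analysis.

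**What to change.** 1. Reconcile the Power Analysis with the Analyses section. While the two studies remain the cited source, use 19% as the maximum loss. Otherwise remove the attribution and justify 15% from other data, such as the centre's own retention.
2. State whether .25 is d, dz or f, and which pre-post correlation applies to the Aim 1 main effect.
3. Restate Aim 1 power as one consistent set. For example, assuming d=.25 and r=.25 (a value that the plan gives only for the interaction): .94 with no loss, .90 at 15% and .89 at 19%.
4. Recompute the medication-interaction power at N=243 and the Aim 3 power at about N=122, with the effect-size type stated for each.

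The cost is a short recalculation and a few sentences. The restated Aim 1 powers will be slightly less favourable if the d=.25, r=.25 reading is adopted. Recruitment, design and analysis methods stay as they are.

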Adolescents will be evaluated for treatment non-response to the BEI at 6, 9, 12, 15, and 18 months posttreatment. Non-response is defined as non-normative use of alcohol, marijuana, or other drugs in the past 90 days. Alcohol and marijuana are the outcomes of interest in this study; however, non-normative use of any psychoactive substance will be considered non-response. Alcohol use norms by age are presented in Table 4 and any marijuana use in adolescence is considered non-normative (NHSDAH, 2007). Tobacco and caffeine products are excluded from consideration. For alcohol, marijuana, and other drugs, frequency and quantity of substance use will be collected for the past 90-days using the Substance Use Questionnaire (SUQ). Adolescents who do not demonstrate a response to the BEI at the 6, 9, 12, 15, or 18 month assessment (i.e., use substances at non-normative levels) will be randomized to either (1) No Additional Treatment Monitoring Group, (2) Parent Training/Adolescent CBT (PT/ACBT; e.g., 12 weeks of parent training and adolescent CBT) (3) PT/ACBT plus concurrent stimulant medication (PT/ACBT+MED). Adolescents who demonstrate immediate initial response will be released from treatment and assigned to a monitoring condition in which they are reassessed at 9, 12, 15, and 18 months. Any adolescent who demonstrates non-normative use at any of the follow-up assessments as defined above will be immediately eligible for randomization to further treatment (as detailed above). Adolescents and parents will complete an assessment battery at the randomization point as outlined in Table 5 unless randomization occurs immediately following the 6 or 12 month assessment (in which case the measures will not need to be repeated).

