Aim 1: We will investigate response to a brief early intervention (BEI) for substance use among adolescents with ADHD. We hypothesize that approximately 50% of adolescents will show meaningful response to the BEI, as evidenced by no more than normative substance use assessed at 6-months following treatment. Aim 2: We will also test whether key variables associated with ADHD (ADHD symptoms) and with the development of substance use (parental monitoring, social impairment, academic functioning, family conflict, deviant peer affiliation and peer drug use, risky sexual behavior, delinguency, teen motivation and selfefficacy) predict response to the BEI. It is expected that poor response to treatment will be associated with high ADHD symptomatology, concurrent delinquency, risky sexual behavior, deviant peer affiliations, academic impairment, family conflict, lack of parent monitoring, poor self-efficacy and high motivation to use substances. Aim 3: We will also examine relative efficacy between the randomized second level interventions for BEI nonresponders (i.e., no treatment control, augmented psychosocial treatment (PT/ACBT) and combined medication and PT/ACBT) for non-responders to the BEI treatment. Adolescents who do not respond to the BEI and are randomized to the intervention arms of (PT/ACBT) or combined intervention (PT/ACBT+MED) will show differential improvements in primary and secondary outcomes (see Table 5). We hypothesize that relative to the no treatment control group, both groups will show improvements, with the largest effects for those who receive PT/ACBT+MED. Secondary analyses will be conducted for the one-year follow-up assessment for all groups. It is expected that therapeutic gains will extend through the follow-up period. Secondary analyses of treatment-related changes in the associated variables listed above will examine whether these changes mediate improvements in substance use. Analyses

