Aim 3: The third aim is to determine if, given nonresponse to the BEI, it is preferable to augment treatment with enhanced psychosocial intervention or multimodal treatment. As previously stated, we expect less than 50% of the sample to respond to the BEI, leaving at least 150 treatment-resistant adolescents to be randomized into one of the three treatment arms: (1) No treatment, (2) PT/ACBT, (3) PT/ACBT + MED. Using the general linear modeling techniques as implemented by SAS PROC GLM, we will examine differences between the treatment arms over post-treatment and one year follow-up measurement points with fixed effects of treatment arm. Analyzing each time period will address separate questions about the effect of intervention immediately post-treatment and at one-year follow-up. For these analyses, mixed linear models and/or GEE strategies will be used (Hedeker et al., 2006). Primary and secondary outcome measures will be evaluated separately (see Table 5). As our sample size permits, as a secondary analysis, we will also examine whether changes in the secondary outcomes listed above following treatment mediate response to treatment and substance use during the follow up phase.

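### Aim 3's stated .90 power at effect size .40 does not apply to its arm-to-arm questions: with 150 split over three arms, pairwise power at one time point is about .44

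*Combined protocol and SAP*

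**What the plan says.** In the combined protocol and SAP, the Power Analysis paragraph gives Aim 3 one figure: "a sample size of 150 with a maximum drop-out rate of 15% will provide .90 power for a treatment effect size of .40". It calls .40 adequate because similar treatments mostly show effect sizes of .40 to .80, and it concludes that the sample is large enough to detect treatment effects. For Aim 3 it names no test, contrast, effect-size metric, allocation ratio, alpha or correlation. Two-tailed .05 is stated for Aim 1. A correlation of .25 is stated for the medication-interaction analysis under Aim 1.

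The Aim 3 analysis paragraph makes 150 a total and a minimum: non-response is expected to run at a rate "leaving at least 150 treatment-resistant adolescents to be randomized into one of the three treatment arms". It frames the question as whether "it is preferable to augment treatment with enhanced psychosocial intervention or multimodal treatment". The Aim 3 hypothesis adds that "relative to the no treatment control group, both groups will show improvements, with the largest effects for those who receive PT/ACBT+MED".

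On the analysis itself, the plan says "we will examine differences between the treatment arms over post-treatment and one year follow-up measurement points with fixed effects of treatment arm". It then says "Analyzing each time period will address separate questions about the effect of intervention immediately post-treatment and at one-year follow-up", and that "mixed linear models and/or GEE strategies will be used". No power is given for any comparison between two arms.

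**The concern.** A reader will take .90 at .40 as the chance of detecting a .40 SD difference between two arms, because that is how the hypotheses are posed. Only about a third of the 150 are in each arm, so a two-arm comparison uses about 85 analysed participants.

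Aim 3 is the trial's only randomised comparison, and this sentence is its only sample-size support. If pairwise power at .40 is about half the stated value, a non-significant result is likely even when a .40 effect is real. A reader relying on the .90 could then take that result as evidence against the augmented treatments.

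**Working it through.** **Inputs.** From the documents: 150 randomised, three arms, 15% loss, effect size .40. Assumed: .40 is a standardised mean difference d (the .40 to .80 benchmark suggests this), 1:1:1 allocation, a normal outcome, and two-sided .05 carried over from Aim 1.

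Analysed per arm: 150 × .85 / 3 = 42.5. At 19% loss: 150 × .81 / 3 = 40.5.

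**Can the stated .90 be reproduced?** The settings found near it are:

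| Setting | Power |
|---|---|
| 150 per arm (127.5 analysed), pairwise d=.40 | .89 |
| Three-arm omnibus F, one time point, arms at 0, .40, .80 | .91 |
| Arm-by-time interaction, 3 arms × 2 times, f=.20, r=.25, N=127 | .91 |

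- The 150-per-arm setting contradicts the Aim 3 analysis paragraph.
- In the omnibus setting, each .40 step still has pairwise power of only .44.
- The interaction setting has noncentrality f²·N·2/(1−r) = .04 × 127 × 2 / .75 = 13.5. Here f=.20 corresponds to a gap in change between extreme arms of .40/.471 = .85 SD (two arms equal) to .40/.408 = .98 SD (arms evenly spaced). For a true .40 SD difference in change, the same test has power .32 (changes 0, .4, .4) or .25 (0, .2, .4).
- If .40 were Cohen's f, the one-time-point omnibus test would give .98, not .90.

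**Pairwise, one time point.** The noncentrality is d/√(2/n), with n per arm. At n=42.5 it is .40/√(2/42.5) = 1.84, and the noncentral t distribution on 83 df gives .445.

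| Case, d=.40 | Power |
|---|---|
| 50 per arm (no loss) | .51 |
| 42 to 42.5 per arm (15% loss) | .44–.45 |
| 40.5 per arm (19% loss) | .43 |
| Baseline-adjusted, variance × (1−r²), r=.25, 42.5 per arm | .47 |
| Same, assumed r=.5 | .56 |

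At 42.5 per arm unadjusted, power is .78 at d=.60 and .95 at d=.80. The chance that both active arms differ significantly from control, each at .40, is about .28 (simulated, 42 per arm).

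**Baseline-adjusted mean of both follow-ups.** The variance factor is (1+ρ)/2 − r², with r the baseline correlation and ρ the correlation between follow-ups. All of these correlations are assumed for Aim 3.

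| r, ρ | Factor | Pairwise | Active arms pooled v control |
|---|---|---|---|
| .25, .25 | .5625 | .68 | .80 |
| .25, .5 | .6875 | .59 | .72 |
| .25, .7 | .7875 | .54 | .66 |
| .5, .5 | .500 | .73 | .85 |
| .5, .7 | .600 | .65 | .78 |

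Pooling cannot answer the psychosocial-versus-multimodal question. These ranges are not bounds: r=.6 with ρ=.5 gives .83 pairwise. Reaching .90 pairwise needs a correlation of about .83 at one time point, or about .75 throughout with both follow-ups.

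**Omnibus arm test.** At one time point, power is .45 for arms at 0, .40, .40 and .35 for 0, .20, .40. On the mean of both follow-ups, over the same correlations, it is .55 to .76 and .43 to .63.

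**What the sample can detect.** For .90 pairwise power at one time point, with 15% to 19% loss, the detectable difference is .71 to .73 SD unadjusted, .69 to .71 at r=.25, and .62 to .63 at assumed r=.5. To detect .40 unadjusted, 133 analysed per arm are needed: 133/.85 = 156.5, so 157 × 3 = 471 randomised, against 300 enrolled.

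**Precision.** The 95% CI half-width for a pairwise difference at 42 per arm is 1.99 × √(2/42) = .43 SD, or .42 at r=.25. An observed zero would not exclude .40 in either case. It would at assumed r=.5 (half-width .38).

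**The case against.** The strongest reply is that the .90 was computed for a different test and is correct for it. Halving d=.40 gives f=.20, the usual two-group conversion. With the only correlation in the documents and 127 analysed, a three-arm by two-time interaction has power .91. The hypothesis speaks of differential improvement, which suits such a test. Aim 1 gives partial support: as a paired test with d=.25 and r=.25, its .90 at 255 participants reproduces, although its .96 at 300 comes out as .94. This may well be where the figure came from. It does not help the stated questions, because that interaction corresponds to .85 SD or more between extreme arms.

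Second, the combined arm is predicted to do best. With arms at 0, .40 and .60 the omnibus test has power .70 at one time point and .81 to .95 on both follow-ups. At 0, .40 and .80 the combined arm against control has .95. These figures are right, but they rest on effects above .40 for the combined arm. Any contrast of .40 stays weak.

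Third, 150 is a floor. Participants who exceed normative use at a later follow-up "will be immediately eligible for randomization to further treatment", so more may be randomised. At 15% loss, one-time-point pairwise power is .52 with 180 randomised, .58 with 210 and .74 with all 300. With all 300 and baseline adjustment it is .76 at r=.25 and .85 at assumed r=.5; adding both follow-ups gives .83 to .96. The power sentence nevertheless claims .90 at 150.

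Finally, the outcomes are days of use in 90 days, and the plan allows transformations and robust tests. Normal-theory figures are therefore approximate, as is any .90 computed in the same way.

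**Conclusion.** The concern holds. The stated .90 at .40 does not carry over to Aim 3's own comparisons. At 150 randomised and 15% loss, pairwise power at one time point is about .44, and .47 to .56 with baseline adjustment at r=.25 to .5. The more favourable reading, an adjusted mean of both follow-ups, gives .54 to .73 at the assumed correlations. The conclusion that the sample is sufficient is not supported for Aim 3 at .40. Unadjusted pairwise power is .78 at .60 and .95 at .80, so the shortfall lies at the low end of the plan's own range, which is the effect it chose.

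This rests on reading .40 as d, on equal allocation, a normal outcome and two-sided .05 without multiplicity adjustment. It does not show that the sponsor's calculation was wrong for whatever test was used, since the documents do not identify that test.

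**What to change.** Restate the Aim 3 power sentence with its test, contrast, allocation and correlation. For example: with at least 150 randomised (1:1:1 assumed) and 15–19% attrition, about 40 to 42 per arm are analysed. For a pairwise difference at one time point (two-sided .05), power at d=.40 is about .43–.44. With baseline adjustment it is .45–.47 at r=.25 and about .54–.56 if r=.5, an assumption. The difference detectable with .90 power is about .71–.73 SD unadjusted, .69–.71 SD at r=.25 and .62–.63 SD if r=.5.

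If the mean of both follow-ups is the intended estimate, say so and state its correlations; power is then about .54–.73 with 15% loss. If an omnibus or arm-by-time test was used, name it and the between-arm difference it implies. Remove the sufficiency claim for Aim 3 at .40, and preferably say that null results will be read from confidence intervals.

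A separate minor point: the 15% maximum dropout is credited to two studies that the Analyses section reports at 16–19%. Use those figures or explain the 15%. The effect on power is about .02.

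The cost is one reworded paragraph, with no extra participants and no change to analysis or conduct. The stated power becomes less favourable.

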Concerta was chosen as the stimulant medication to remain consistent with Riggs and colleagues' (2011) major medication trial in adolescents with combined ADHD and established substance use disorder. Optimal dose will be defined as one enabling adolescents to reach a level of home/school functioning considered good with no further room for improvement that represents a meaningful change from baseline with a tolerable level of side effects. A similar definition has been employed in the MTA and other large ADHD trials (Vitiello et al., 2001, Palumbo et al., 2008, Collins et al., 2006). All adolescents in this arm will start the protocol taking medication seven days a week (no drug holidays). Adolescents who have not previously taken stimulant medication for ADHD will be started on the lowest available dose of Concerta (18mg which approximates 5mg TID of MPH). Adolescents who are already taking medication for ADHD at the time of randomization will have a consultation with the study doctor to determine whether their current medication can be safely continued with the study medication or whether changes are needed (e.g., safely withdrawing the other medications, reducing dose, etc.) prior to initiating the study medication. After one week, parents and teens will rate efficacy and tolerability using parent symptom rating scales, the parent and teen versions of the Impairment Rating Scale (IRS) and the Clinical Global Impression Scales for ADHD (CGI; Rapoport et al., 1985). The Pittsburgh Side Effects Rating Scale (PSERS) will be used to assess drug tolerability. At each medication assessment visit, a study physician will meet with the family to review the efficacy and tolerability ratings and complete the ADHD CGI-I/S (Improvement and Severity Scales) to determine the need for a dose change. The assessing clinician will be instructed to increase the dose (to 36mg, 54mg, then 72mg, respectively) unless the physician believes the subject's functioning has been optimized (CGI-S <3) or the teen cannot tolerate a higher dose. This threshold has been found to be a valid definition of optimal dose (Gao et al., 2006). This process will be repeated in one-week intervals until the lowest effective dose that is well-tolerated has been identified. We chose a one week duration for each dose to allow for a thorough assessment of the therapeutic effects of that dose and timely collection of ratings from home. These one-week follow-up appointments may take place in

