Risk: Participants may experience adverse events related to medication. **Procedure:** While ADHD medication will not occur for all participants, all participants must be able to tolerate stimulant medication to participate in the study. Therefore, the side effect profile of ADHD medications will be reviewed with families during the consent process. Participants with a documented history of intolerance to all approved ADHD medications will be excluded from the study. All participants will undergo structured assessments of psychiatric comorbidity at baseline as well as medication tolerability which should further reduce the rate of serious adverse events For individuals randomized to the psychosocial treatment and medication arm of the study, height, weight, resting blood pressure and pulse will be collected at each following assessment. All of these procedures should minimize the risk of serious adverse events. Each personal care physician's office has their own procedures for handling emergencies, including a 24 hour on call system. To ensure the safety of all participants, [name] (the study psychiatrist and a board certified child psychiatrist) will be available by pager 24 hours a day during medication phases of the study.

Confidentiality Assurances

In virtually all instances, research data collected in the study will be kept strictly confidential and will not be shared with anyone outside of the research team, including referring schools and care providers. The only exceptions to confidentiality, which will be clearly specified in the consent form, will be for information related to medical emergencies, current child abuse or neglect, or imminent risk of death or serious injury to the participant or others. All research materials will be encoded by a research number and will contain no other identifying information. Written materials will be maintained in locked filing cabinets or storage boxes and computer spreadsheets will be saved in protected files requiring a password for access.

Potential Benefits

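### Structured tolerability assessment is claimed for all participants, but the only side-effect scale is described for one arm, with no pre-dose rating specified

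*Combined protocol and SAP*

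**What the plan says.** The Potential Risks section, under adverse events related to medication, says: "All participants will undergo structured assessments of psychiatric comorbidity at baseline as well as medication tolerability", and adds of these assessments: "which should further reduce the rate of serious adverse events". The next sentence limits repeated body-size and vital-sign measurements to the medication arm.

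The procedure itself is in the Concerta paragraphs under Interventions. Their scope is the PT/ACBT+MED arm: "All adolescents in this arm will start the protocol taking medication seven days a week". On timing they say: "After one week, parents and teens will rate efficacy and tolerability using parent symptom rating scales". The instrument is then named: "The Pittsburgh Side Effects Rating Scale (PSERS) will be used to assess drug tolerability". A study physician reviews the ratings with the family at each medication assessment visit, and the cycle repeats weekly while the dose is adjusted.

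Tolerability enters the dose decision twice. Escalation continues unless functioning is judged optimised "or the teen cannot tolerate a higher dose". The optimal dose is defined by a level of functioning "that represents a meaningful change from baseline with a tolerable level of side effects".

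The same section provides for an in-person initial medication visit with a brief medical exam. Table 5, the schedule of measures, has no side-effect row at any visit.

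**The concern.** A safety measure credited in the risk section should be traceable to a procedure: who is rated, with what, and when. Here the statement covers everyone, while the described procedure covers one of three randomised arms and nobody outside the randomised phase.

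The second issue is interpretation within the medication arm. A side-effect scale records complaints, not their cause. If the first rating is made after a week on drug, a complaint already present before dosing looks the same as one that began with the drug. Such a complaint could be read as intolerance and hold the dose down, or a real drug effect could be put down to a long-standing complaint. Any side-effect table for this arm would carry the same ambiguity.

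**Working it through.** The protocol gives no figure on this point, so there is nothing to reproduce. The check sets the passages side by side, with one piece of arithmetic on coverage.

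**Step 1: who is assessed.** Potential Risks says all participants. The PSERS appears once, in text confined to PT/ACBT+MED. Loose drafting is a weak explanation, because the very next sentence in Potential Risks narrows another measurement to the medication arm.

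**Step 2: when.** The words "at baseline" in the risk sentence may attach only to psychiatric comorbidity, so the sentence is not a clear promise of a baseline tolerability scale. The mismatch survives either reading, since no side-effect scale is described for all participants at any time point. In the medication arm the earliest rating with a stated time is one week after starting.

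**Step 3: what the schedule adds.** Table 5 has no PSERS or other side-effect row at intake, at the randomization visit, or at any later assessment. It lists a parent Treatment History Form, but the form's content is not given, so it neither supplies nor rules out tolerability information.

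**Step 4: the two parts of optimal dose.** Functioning has a pre-drug reference. Table 5 schedules parent and adolescent Impairment Rating Scales at the 6- and 12-month assessments, and at the randomization visit for families randomised after the 9-, 15- or 18-month screens. Side-effect complaints have no equivalent pre-drug rating. The initial medication visit provides weight, blood pressure, heart rate and similar signs, which do not record symptom complaints.

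**Step 5: coverage.** Inputs:
- total sample 300 (Participants);
- at least 150 randomised to three arms (Analyses, Aim 3);
- equal allocation, which is an assumption because no ratio is stated.

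For R randomised, the share of participants with a described PSERS is (R / 3) / 300.
- R = 150: 150 / 3 = 50, and 50 / 300 = 17%.
- R = 300 (the upper limit): 300 / 3 = 100, and 100 / 300 = 33%.

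Either share is well short of all participants.

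**The case against.** The strongest reply has four parts.

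- The risk sentence sits among screening statements, so tolerability for all participants could mean tolerability history taken at entry.
- Absence from Table 5 proves little. The table also omits the Clinical Global Impression scale, the vital signs and the treatment-satisfaction measures, so it appears to leave out measures tied to treatment and medication visits in general.
- The sentence naming the PSERS carries no time limit. A pre-dose rating is unstated, not excluded.
- Dose decisions rest on a physician's judgement after meeting the family, not on a change score. Weekly ratings also let each later dose be compared with the one before.

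All of this is fair, and it rules out two stronger conclusions that a reader might draw. The first is that tolerability decisions have no reference at all. The initial exam, the within-person comparison across doses and the clinician's review are all references, and the dose rule as written does not require a side-effect baseline. The second is that the trial must collect the PSERS in all three arms. No aim, hypothesis or analysis sets out to estimate a drug-attributable side-effect rate. Comparison-arm ratings at post-treatment or at one year would not resolve what happened in week 1. Non-response is also known only from the results of the triggering assessment, so rating teens at that point would mean giving the form to everyone still being screened.

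What stands is narrower. A claim made for everyone has no matching described procedure. The comparison between successive doses starts from an on-drug rating, so it cannot show which complaints were there before the drug.

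**Conclusion.** The point holds in limited form. Potential Risks relies on a structured tolerability assessment of all participants that the Interventions text and Table 5 do not provide; the described PSERS reaches about 17% of the sample at 150 randomised and 33% at most, assuming equal allocation. In the medication arm no pre-dose side-effect symptom rating is specified, so on the PSERS a complaint that predates the drug cannot be separated from a drug effect when tolerability is judged during dose adjustment.

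The number of teens whose complaints would be misattributed cannot be estimated, because the documents give no pre-dose complaint rate. The primary substance-use analysis does not depend on this point. It is a modest gap in safety measurement and an inconsistency between sections, worth correcting because the participants are minors and the correction is cheap.

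**What to change.** 1. State in the Interventions section that the PSERS is completed at the existing in-person initial medication visit, before the first dose of study drug.
2. Report medication-arm side effects descriptively as change from that rating, alongside the on-drug ratings. Record whether the teen was taking another ADHD medication at the time. For those teens the change compares study drug with prior treatment, not with no treatment. If some participants have already started study drug, report them separately without a change score.
3. Reconcile the Potential Risks sentence with the Interventions text and Table 5. Either state which participants receive which tolerability measure and when, or limit the sentence to the medication arm. Add the PSERS to Table 5, or note under the table that medication-visit measures are listed elsewhere.

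The cost is one additional form per teen in the medication arm, at a visit already scheduled and on a scale already used in that arm, plus a few lines of text and one descriptive table. This changes measurement and reporting only; no dose or clinical rule is proposed.
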